9.1 Covariates and Subgroups

9.1.1 PLANNED COVARIATES

9.1.2 SUBGROUPS

Summary statistics for the primary efficacy endpoint will be provided for baseline and demographic characteristics such as iris pigmentation, age, gender, race, and ethnicity. The primary analysis model, as specified below, will be attempted; however, given small subgroup sample sizes, non-convergence may be expected.

9.2 Interim Analyses

No interim analyses are planned.

9.3 Partial or Missing Dates

The following conventions will be used to impute missing portions of dates for adverse events and concomitant medications, if warranted. Note that the imputed values outlined here may not always provide the most conservative date. In those circumstances, the imputed value may be replaced by a date that will lead to a more conservative analysis.

A. Start Dates

- 1) If the year is unknown, then the date will not be imputed and will be assigned a missing value.
- 2) If the month is unknown, then:
 - i) If the year matches the first dose date year, then impute the month and day of the first dose date.
 - ii) Otherwise, assign 'January.'
- 3) If the day is unknown, then:
 - i) If the month and year match the first dose date month and year, then impute the day of the first dose date.
 - ii) Otherwise, assign the first day of the month.

B. Stop Dates

- 1) If the year is unknown, then the date will not be imputed and will be assigned a missing value.
- 2) If the month is unknown, then assign 'December.'
- 3) If the day is unknown, then assign the last day of the month.

Unless having an end date before the first administration of the study drug, an adverse event with a completely missing start date will be interpreted as started between the first dose date included and

recovery to a satisfactory state, or stabilization, or appropriate outcome is established as judged by the Investigator (included), or the analysis cut-off date included, whichever comes first.

A medication with a completely missing start date will be interpreted as started before the first dose date. A medication with a completely missing end date will be interpreted as ongoing at the time of data extraction (and therefore being not stopped before the first dose).

10. Analysis Populations

Analysis populations include the ITT population, the per-protocol (PP) population, and the safety population. The statistical analysis of safety data will be performed on the safety population. The analysis of efficacy data will be performed on the ITT population, and, separately, on the PP population as a sensitivity analysis.

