9 ADVERSE EVENTS

9.1 Adverse Event

For the purposes of the trial, an adverse event is defined as any untoward medical event occurring after signing of the informed consent until exited from the trial. An adverse event can therefore be any unfavorable and unintended sign, symptom, or disease occurring after the subject started the clinical trial, without any judgment about causality. Any pre-existing medical condition that worsens during the trial will also be considered a new adverse event. Documentation regarding the adverse event should be made as to the nature, date of onset, end date, severity, relationship to study procedure, expectedness, action(s) taken, seriousness, and outcome of any sign or symptom observed by the investigator or reported by the patient upon indirect questioning.

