17.1 Adverse Events

An adverse event is defined as any untoward medical occurrence associated with the use of an test article in humans, whether or not considered test-article-related. An adverse event can be any unfavorable and unintended sign (e.g., an abnormal laboratory finding), symptom, or disease temporally associated with the use of test article, without any judgment about causality. Exacerbation of conditions related to the signs and symptoms of dry eye disease will not be reported as an adverse event. The adverse event reporting period ends upon trial exit. Study drug includes the investigational drug under evaluation.

All adverse events will be coded using MedDRA Version 27.0 (or higher).

Treatment-emergent adverse events (TEAEs) are defined as any adverse event that occurs or worsens on or after the first dose of study treatment. Adverse events recorded in the eCRF which began prior to treatment will not be included in the summary tables but will be included in the adverse event data listings.

An overall summary will be presented that includes the number and percentage of subjects who experienced at least one AEs, ocular AEs, non-ocular AEs, SAEs, AEs by maximal severity, AEs by relationship to study procedure, AEs leading to treatment discontinuation, and AEs resulting in death by treatment arm for the Safety Population. In addition, overall TEAEs and the number and percentage of subjects who experienced at least one TEAE, ocular TEAEs, non-ocular TEAEs, TE-SAEs, TEAEs by maximal severity, TEAEs by relationship to study procedure, TEAEs leading to treatment discontinuation, and TEAEs resulting in death by treatment arm for the Safety Population.

Separate summaries will be provided for the following categories of AEs:

- Ocular AEs by SOC and PT
- Non-ocular AEs by SOC and PT

- Ocular TEAEs by SOC and PT
- Non-ocular TEAEs by SOC and PT
- Instillation Site Ocular TEAEs by Duration of Time
- Ocular TEAEs by SOC, PT, and maximal severity
- Non-ocular TEAEs by SOC, PT, and maximal severity
- Ocular TEAEs by SOC, PT, and strongest relationship to study procedure
- Non-ocular TEAEs by SOC, PT, and strongest relationship to study procedure
- Ocular TEAEs by SOC, PT, maximal severity, and strongest relationship to study procedure
- Non-ocular TEAEs by SOC, PT, maximal severity, and strongest relationship to study procedure
- TEAEs That Led to Premature Treatment Discontinuation
- SAEs

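### SAP 9.3 can impute an adverse event's start after its known stop date and so label an event that resolved before dosing as treatment-emergent

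*SAP*

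**What the plan says.** SAP 9.3 sets these rules for adverse event dates.

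- Start, day missing: "If the month and year match the first dose date month and year, then impute the day of the first dose date". Otherwise the first of the month is used.
- Start, month missing: "If the year matches the first dose date year, then impute the month and day of the first dose date". Otherwise January is used.
- Stop, day missing: "If the day is unknown, then assign the last day of the month".
- Stop, month missing: "If the month is unknown, then assign 'December"; with the day rule this becomes 31 December.

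Only one sentence compares an end date with dosing. It opens "Unless having an end date before the first administration of the study drug, an adverse event with a completely missing start date" and then treats such an event as starting on or after the first dose. It does not mention partial start dates. The section applies its conventions only where warranted and adds an option: "In those circumstances, the imputed value may be replaced by a date that will lead to a more conservative analysis".

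Protocol 9.1 collects events "occurring after signing of the informed consent until exited from the trial", so an event can begin and resolve before randomization. SAP 17.1 counts as treatment-emergent any event that starts or worsens on or after the first dose of study treatment, and keeps events that began earlier out of the summary tables. Protocol 10.9 ties the definition to randomized treatment. SAP 17.1 also states "The adverse event reporting period ends upon trial exit", whereas Protocol 9.5 has events still ongoing at the end followed by telephone until they are resolved or stable.

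**The concern.** The SAP protects the event with no start date at all and leaves unprotected the event whose start month is known. For the second kind, a recorded stop before Day 1 proves that the event was over before randomized dosing, yet the rule moves its start to the dosing date. The result is a start later than the stop, a negative duration, and a treatment-emergent label that the subject's own record contradicts.

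The stop-date rules have a milder fault. Nothing limits the imputed date to the period in which the subject was observed, so a duration computed from it can be far too long.

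What is at stake is the accuracy of the treatment-emergent counts and of the listings. With about 55 subjects per arm (Protocol 4), one wrongly labelled subject moves an arm's rate by 1/55 = 1.8 percentage points.

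**Working it through.** The plan gives no figure to reproduce. The check applies the rules literally to dates. The documents give no dosing dates, so all calendar dates are assumptions (year 2024, after the protocol date of 19 April 2024).

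**Inputs from the documents**

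- Visit 1 is nominally Day -14 and there is no Day 0 (SAP 5.1), so Visit 1 falls 14 days before Day 1. The protocol window (-16/+2 days) gives a gap of 12 to 30 days; the SAP window gives 14 to 16.
- Exit is Visit 3, Day 2, one day after the first randomized dose.
- First dose is read as the first randomized dose on Day 1, as in Protocol 10.9.

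**Formulas**

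- Duration = stop - start + 1 day.
- Treatment-emergent if start is on or after the first dose date (SAP 17.1).

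**Example**

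Assume first dose on 20 May, Visit 1 on 6 May and exit on 21 May. The event is recorded as start May (day unknown), stop 12 May.

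1. Month and year match the first dose, so the imputed start is 20 May.
2. Start minus stop = 20 - 12 = 8 days: the event starts 8 days after it ended.
3. Duration = 12 - 20 + 1 = -7 days.
4. The start equals the first dose date, so the event is treatment-emergent.
5. If the start is known only as 2024, the month-missing rule gives the same result.
6. If the start were completely missing, the guard sentence would apply and the event would not be placed after dosing.

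**How often the date pattern triggers the fault**

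Take every start/stop pair lying between Visit 1 and the day before Day 1, for each assumed Day 1 from 20 May to 30 December 2024 (225 dates). The day-missing rule puts start after stop whenever the true start falls in the same month as Day 1.

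| Gap, Visit 1 to Day 1 | Pairs | Start after stop, day missing | Most negative duration (1 - gap) |
|---|---|---|---|
| 12 days | 17,550 | 74% | -11 days |
| 14 days | 23,625 | 70% | -13 days |
| 16 days | 30,600 | 66% | -15 days |
| 30 days | 104,625 | 35% | -29 days |

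With the month missing as well, the share is 100%, because every pair lies in the same calendar year as Day 1. These are shares of possible date pairs, given a partial start and a known stop before dosing. They are not expected event frequencies.

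**Stop dates**

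With exit on 21 May, a stop recorded as May becomes 31 May, 31 - 21 = 10 days after exit. A stop recorded only as 2024 becomes 31 December, 224 days after exit. For first doses from 1 May to 31 October, exits run from 2 May to 1 November, and the December rule overshoots exit by 243 down to 60 days.

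**The case against.** The strongest reply is that the SAP already leaves room to do the right thing. The conventions apply only where warranted, a more conservative date may be substituted, and SAP 17.1 keeps events that began before treatment out of the summary tables. An event that ended before dosing must have begun before dosing, so a careful programmer would not need an imputed start to classify it. This stands in part: correction is possible. But none of these provisions requires the start to be no later than the stop. The substitution is optional, and the SAP does not say what conservative means; for counts of treatment-emergent events it would often be taken to favour keeping the event in.

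A second reply is that exposure is small. Dosing is in clinic, adverse events are queried before randomization at Visit 2, edit checks are planned, and queries are resolved before lock. This stands, and it limits the point to a minor one. Events that resolved before dosing also precede treatment, so mislabelling should not systematically favour either masked arm.

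A reader might infer more than the documents support:

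- **That any stop date after exit is impossible.** It is not, because Protocol 9.5 follows ongoing events. Only negative durations are impossible.
- **That the planned table of instillation-site events by duration will be corrupted.** This is remote: instillations are given by site staff on known dates, and nothing says the table uses imputed dates.
- **That medication summaries are distorted.** SAP 14.2 classifies medications by end date and by use relative to Visit 1, so an imputed start on the first dose date changes no planned summary.

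**Conclusion.** The fault holds as a gap in a stated rule. Applied literally, SAP 9.3 can place the start of an adverse event after its known stop and label an event that resolved before dosing as treatment-emergent. It needs two conditions together: a partial start date whose known parts match the first dose, and a recorded stop before Day 1. The number of such events cannot be derived from the documents and is probably small. Uncapped stop dates are a secondary weakness that can inflate durations.

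The conclusion rests on first dose meaning the first randomized dose. SAP 9.3 does not define the term, and SAP 15.2 counts exposure from Visit 1, when every subject receives vehicle. If the Visit 1 dose were meant, the pre-dose window would almost vanish and screening events would be treatment-emergent by definition, contrary to Protocol 10.9. That ambiguity needs settling in any case.

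Severity is minor. Safety tables and listings are affected; the efficacy analysis is not.

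**What to change.** In SAP 9.3:

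1. Extend the existing guard to partial start dates. If the known stop date is before the first randomized dose, impute the earliest start consistent with the recorded parts (not before consent for an event recorded as new on trial, and never after the stop date), and class the event as not treatment-emergent. In the example, with consent at Visit 1 on 6 May, the start becomes 6 May and the duration 12 - 6 + 1 = 7 days.
2. Cap imputed adverse event stop dates at the later of trial exit and the last follow-up contact.
3. State that first dose date in this section means the first randomized dose, consistent with Protocol 10.9.

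The medication rules need no change on this account. The cost is a few lines of SAP text and matching code, settled before unmasking. No data collection changes.

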10.1 Intent-to-Treat

The ITT population includes all randomized subjects. Subjects in the ITT population will be analyzed as randomized.

10.2 Per Protocol

The PP population includes subjects in the ITT population who received at least one dose of test article, who met all inclusion/exclusion criteria, and who did not incur a major protocol deviation. Protocol deviations will be assessed prior to database lock and unmasking. Subjects in the PP population will be analyzed as treated.

10.3 Safety

The safety population includes all randomized subjects who have received at least one dose of the test article. Subjects in the safety population will be analyzed as treated.

11. General Statistical Considerations

11.1 Unit of Analysis

Safety points will be analyzed for both eyes separately. Both eyes separately will be included in the statistical models that evaluate efficacy.

11.2 Missing or Inconclusive Data Handling

[REDACTED]

[REDACTED]

[REDACTED]

[REDACTED]

[REDACTED]

[REDACTED]

[REDACTED]

[REDACTED]

[REDACTED]

11.3 Baseline Definitions

[REDACTED]

[REDACTED]

[REDACTED]

[REDACTED]

[REDACTED]

[REDACTED]

[REDACTED]

[REDACTED]

12. Disposition of Subjects

Subject disposition will be presented in terms of the numbers and percentages of subjects who were randomized, completed the trial, and discontinued from the trial. Subjects who are not discontinued from the trial will be considered trial completers. Disposition descriptive statistics, primary counts, and percentages will be summarized. Disposition information will be presented for the ITT population. In general, percentages will be calculated using randomized subjects as the denominator (with any exceptions noted).

The number and percentage of subjects prematurely discontinued from the trial and the reasons for trial discontinuation will be summarized for all randomized subjects. The reasons for trial discontinuation that will be summarized include adverse event, lost to follow-up, physician decision, protocol violation, study terminated by Sponsor, withdrawal by subject, and other. A subject listing will be provided that includes the date of and reason for premature trial discontinuation.

The number and percentage of subjects with major protocol deviations will be summarized by treatment for all randomized subjects. The protocol deviations that will be summarized include: informed consent, inclusion / exclusion and randomization, test article / study drug Instillation and assignment at site, improper protocol procedures at site, site failure to report serious adverse event / adverse event, visit

out of window, subject non-compliance with test article, subject use of prohibited concomitant medication, subject failure to follow instructions, and other. A subject listing will include the date and description of each deviation. In addition, subject listings will include treatment arm, whether inclusion and exclusion criteria were met, and inclusion in the ITT, Safety, and PP populations.

13. Demographic, Baseline Characteristics, and Pretreatment Variables

13.1 Demographic Variables

The demographic and body habitus variables collected in this trial include age, sex, race, ethnicity, iris color, and childbearing potential and . These variables will be descriptively summarized, taking into account treatment arm, for the ITT and safety populations, separately.

Age (years) will be summarized using continuous descriptive statistics. Further, age will be categorized as <65 years or ≥65 years. Age will be reported in years and calculated using the following formula:

$$\text{Age} = (\text{informed consent date} - \text{date of birth}) / 365.25 \text{ truncated as an integer}$$

The number and percentage of subjects will be presented for age category, sex, race, ethnicity, iris color by eye (OD and OS, separately), and for childbearing potential.

A subject listing that includes all demographic variables for the ITT population will be provided.

13.2 Baseline Characteristics

A baseline characteristics table will include descriptive summary statistics for various baseline characteristics for each eye in the ITT and/or safety population. Baseline data for the primary endpoint, staining, and other variables may be included. Other summary methods, such as area under the curve (AUC) or averages for 80 min to 100 min, may be included.

13.3 Pretreatment Variables

Baseline intraocular pressure and visual acuity will be summarized with descriptive statistics for all subjects by eye. Subjects will be grouped by treatment arm.

14. Medical History and Concomitant Medications

14.1 Medical History

Medical history will be coded using MedDRA Version 27.0 or higher.

Non-ocular medical history will be summarized using discrete summary statistics and presented by treatment condition at the subject and event level by System Organ Class (SOC) and Preferred Term

(PT) using the ITT population. Ocular medical history will be similarly summarized at the subject and event level. If a subject reports the same PT multiple times within the same SOC, that PT will only be reported once within that SOC. As with the PT, if a subject reports multiple conditions within the same SOC, that SOC will only be reported once.

Listings of medical history will be generated separately for ocular and non-ocular data.

14.2 Concomitant Medications

Concomitant medications will be coded using WHODrug Global, B3, March 2024 (or higher) and summarized to the therapeutic drug class (Anatomical Therapeutic Chemical [ATC] 4 classification) and preferred name. If the ATC 4 classification is not provided, the next lowest classification that is provided in the coding dictionary will be used. The preferred name will be defined as the active ingredient; if the active ingredient is not provided or includes more than two ingredients (e.g., multivitamins) then the drug name will be summarized as the preferred name. Any uncoded terms will be summarized under the ATC classification and preferred name of “Uncoded.”

Prior medications are defined as those medications listed as having an end date prior to Visit 1.

Concomitant medications are defined as those medications listed as having been taken 1) prior to Visit 1 and continuing for any period of time following Visit 1, or 2) at any time following Visit 1.

Concomitant medications will be summarized using the ITT population by treatment arm. Ocular and non-ocular medications will be summarized separately. Medications will be tabulated for each treatment condition using frequencies and percentages. Subjects may have more than one medication per ATC text. At each level of subject summarization, a subject will be counted once if that subject reports one or more medications. Percentages will be based on the number of subjects in each treatment condition. Listings of prior and concomitant medications will be generated separately for ocular and non-ocular data.

15. Dosing Compliance and Treatment Exposure

15.1 Dosing Compliance

An Investigator will be on-site for dosing and on-call throughout the two-day duration of the trial; thus, significant percentages of major deviations as a result of dosing compliance are not expected.

15.2 Treatment Exposure

Extent of treatment exposure for subjects will be calculated in days using the following:

$$\text{Extent of Exposure (days)} = \text{Date of completion/discontinuation} - \text{date of Visit 1} + 1$$

Extent of treatment exposure for subjects who were lost to follow-up will be calculated in days using the following:

[figure not shown]
[figure not shown]
$$\text{Extent of Exposure (days)} = \text{Date of last recorded visit} - \text{date of Visit 1} + 1$$

The presentation of extent of treatment exposure will use the safety population. A subject listing of treatment exposure will also be produced that will include overall exposure. Descriptive statistics for exposure will be presented by treatment arm for overall exposure, exposure prior to Day 1 and exposure after Day 1.

16. Efficacy Analyses

16.1 Analysis of the Primary Efficacy Endpoint

The primary endpoint will be assessed using the ITT population with observed data only. The ITT population includes all randomized subjects.

16.2 Analysis of the Secondary Endpoints

Not applicable.

16.3 Model Presentation

16.4 Covariance Structures and Convergence

16.5 Efficacy Criterion

16.6 Multiplicity Considerations

Not applicable

17. Safety Analysis

All safety analyses will be conducted using the safety population.

17.1 Adverse Events

An adverse event is defined as any untoward medical occurrence associated with the use of an test article in humans, whether or not considered test-article-related. An adverse event can be any unfavorable and unintended sign (e.g., an abnormal laboratory finding), symptom, or disease temporally associated with the use of test article, without any judgment about causality. Exacerbation of conditions related to the signs and symptoms of dry eye disease will not be reported as an adverse event. The adverse event reporting period ends upon trial exit. Study drug includes the investigational drug under evaluation.

All adverse events will be coded using MedDRA Version 27.0 (or higher).

Treatment-emergent adverse events (TEAEs) are defined as any adverse event that occurs or worsens on or after the first dose of study treatment. Adverse events recorded in the eCRF which began prior to treatment will not be included in the summary tables but will be included in the adverse event data listings.

An overall summary will be presented that includes the number and percentage of subjects who experienced at least one AEs, ocular AEs, non-ocular AEs, SAEs, AEs by maximal severity, AEs by relationship to study procedure, AEs leading to treatment discontinuation, and AEs resulting in death by treatment arm for the Safety Population. In addition, overall TEAEs and the number and percentage of subjects who experienced at least one TEAE, ocular TEAEs, non-ocular TEAEs, TE-SAEs, TEAEs by maximal severity, TEAEs by relationship to study procedure, TEAEs leading to treatment discontinuation, and TEAEs resulting in death by treatment arm for the Safety Population.

Separate summaries will be provided for the following categories of AEs:

- Ocular AEs by SOC and PT
- Non-ocular AEs by SOC and PT

- Ocular TEAEs by SOC and PT
- Non-ocular TEAEs by SOC and PT
- Instillation Site Ocular TEAEs by Duration of Time
- Ocular TEAEs by SOC, PT, and maximal severity
- Non-ocular TEAEs by SOC, PT, and maximal severity
- Ocular TEAEs by SOC, PT, and strongest relationship to study procedure
- Non-ocular TEAEs by SOC, PT, and strongest relationship to study procedure
- Ocular TEAEs by SOC, PT, maximal severity, and strongest relationship to study procedure
- Non-ocular TEAEs by SOC, PT, maximal severity, and strongest relationship to study procedure
- TEAEs That Led to Premature Treatment Discontinuation
- SAEs

Adverse Events and TEAEs will be summarized using discrete summary statistics and presented by treatment arm and all subjects for the the Safety Population. If a subject reports the same PT multiple times within the same SOC, that PT will only be reported once within that SOC. As with the PT, if a subject reports multiple conditions within the same SOC, that SOC will only be reported once. In the summaries, SOCs will be listed in ascending alphabetical order. PTs will be listed in order of descending frequency within each SOC for all subjects.

A missing severity will be considered Severe. 'Drug Related' will be defined as 'Definitely Related', 'Probably related' or 'Possibly Related', excluding 'Unlikely Related' and 'Not Related'. A missing relationship will be considered as 'Definitely Related'.

All AEs, ocular AEs, non-ocular AEs, and SAEs will be presented in subject listings.

18. Other Safety Variables

